12. QUALITY CONTROL AND QUALITY ASSURANCE

12.1. Monitoring

Perrigo has ethical, legal and scientific obligations to carefully follow this study in a detailed and orderly manner in accordance with established research principles and FDA regulations. All medical records (source documents) of the subjects participating in this study must be presented for review and verification of eCRFs.

12.2. Auditing

Perrigo (or representative) may conduct audits at the study center(s). Audits will include, but are not be limited to drug supply, presence of required documents, the informed consent process, and comparison of case report forms with source documents. The investigator agrees to participate with audits conducted at a reasonable time in a reasonable manner.

Regulatory authorities worldwide may also audit the investigator during or after the study. The investigator should contact Perrigo immediately if notified of such an audit and must fully cooperate with the audits conducted at a reasonable time in a reasonable manner.

13. ETHICS AND RESPONSIBILITY

This study must be conducted in compliance with the protocol, the United States Food and Drug Administration (FDA) regulations, any other countries regulations, and ICH GCP Guidelines.

Listing 16.2.7.2 – Adverse Events Leading to Study Treatment Interruption Temporarily/ Study Treatment Discontinued Permanently.....	63
Listing 16.2.7.3 – Serious Adverse Events.....	63
Listing 16.2.8 – Urine Pregnancy Tests (Female Subjects Only).....	64

List of Abbreviations

AE	Adverse Event
ANOVA	Analysis of Variance
[REDACTED]	[REDACTED]
BE	Bioequivalence
CI	Confidence Interval
CMH	Cochran–Mantel–Haenszel Test
IOP	Intraocular Pressure
MedDRA	Medical Dictionary for Regulatory Activities
OH	Ocular Hypertension
PD	Protocol Deviation
POAG	Primary Open Angle Glaucoma
PP	Per-Protocol (Population)
PV	Protocol Violation
SAE	Serious Adverse Event
SAP	Statistical Analysis Plan
TEAE	Treatment-Emergent Adverse Event
TESAE	Treatment-Emergent Serious Adverse Event
WHO Drug	World Health Organization Drug Dictionary

Statistical Analysis Plan

1 Purpose of Statistical Analysis Plan

The purpose of the statistical analysis plan is to describe in detail all the data, statistical methods, and summary tables required to implement the statistical analysis of Clinical Study Protocol PRG-NY-19-001 [REDACTED]

In the event that the protocol has amendment(s) that do not have an impact on the statistical analysis methodology, this SAP will not require an amendment. This SAP has been developed and finalized prior to database lock of the clinical database for Protocol PRG-NY-19-001.

2 Study Objectives

To demonstrate bioequivalence of brinzolamide ophthalmic suspension 1% (Perrigo Pharma International DAC) to Azopt® (brinzolamide ophthalmic suspension) 1% (Novartis Pharmaceutical Corporation) by comparing their efficacy and safety in the treatment of subjects with Primary Open Angle Glaucoma (POAG) or Ocular Hypertension (OH) in both eyes.

3 Study Design and Sample Size

3.1 Study Design

For the purpose of exploring the above objectives, the study will be conducted as a double-masked, randomized, multi-center, active-controlled, parallel-group study.

Each subject will be randomly assigned to one of the following treatment groups [REDACTED]:

- (1) Test: Brinzolamide Ophthalmic Suspension, 1%, Perrigo Pharma International DAC, Ireland, [REDACTED]
- (2) Reference: Azopt® (brinzolamide ophthalmic suspension), 1%, manufactured by Novartis Pharmaceuticals Corporation.

The study consists of a run-in phase and a six-week treatment (42 ± 4 days) period.

At Baseline/Visit 2, eligible subjects who meet all inclusion criteria and do not meet any exclusion criteria will be randomized [REDACTED] to either the test or reference product for the 6-week treatment period. Subjects will apply one drop of either test product or reference product in both eyes three times daily at approximately 08:00 am, 04:00 pm and 10:00 pm for six weeks (42 ± 4 days).

Subjects will come to the study site for clinical evaluations Visit 1/Screening, Visit 2/Day 0 (Baseline), Visit 3/Week 2/Day 14 (± 4 days), and Visit 4/Week 6/Day 42 (± 4 days) (End of Study) or at early discontinuation. Safety will be assessed by monitoring adverse events at each visit.

3.2 Sample Size

4 Analysis Populations

The analysis populations are defined as follows:

- (1) Safety population: all randomized subject who received study product;
- (2) Per Protocol (PP) population: any randomized subject who (a) met all inclusion/exclusion criteria; (b) received and used study medication; (c) met compliance [REDACTED]
[REDACTED] (e) complete IOP evaluations for both eyes at Visit 3/Day 14 (week 2) and Visit 4/Day 42 (week 6) within the designated visit window (i.e. $+\text{-} 4$ days for each visit); (f) have no significant protocol violations that could have interfered with the administration of the treatment or the precise evaluation of treatment efficacy.

Subjects whose condition worsens (e.g., IOP \geq 36 mm Hg in either eye) to a degree that they require alternative or supplemental therapy for the treatment of their primary open angle glaucoma or ocular hypertension during the study, should be discontinued and excluded from the PP population analysis.

5 Planned Analyses

5.1 Methodological Considerations

Tables will have columns corresponding to or be stratified by the treatment groups.

All data will be listed by treatment group, subject and visit/time point where appropriate. The total number of subjects under the stated population (N) will be displayed in the header of summary tables. Efficacy data will be tabulated by site and if obviously inconsistent discrepancies will be observed with the results across all sites, then these differences will be explored and addressed in the final study report.

Data will be summarized using descriptive statistics for continuous variables. Unless otherwise specified, descriptive statistics will include number of subjects, mean, standard deviation, minimum, median and maximum. The statistic "Missing" will also be presented as the number of missing entries/subjects, if any at that visit/timepoint, and presented as a summary statistic only when non-zero. The minimum and maximum statistics will be presented to the same number of decimal places as the original data. The mean and median will be presented to one more decimal place than the original data, whereas the standard deviation will be presented to two more decimal places than the original data.

Categorical variables will be summarized by frequency (n) and percentage (%). Percentage will be obtained as $(n/N) * 100$. Unless otherwise stated, all percentages will be expressed to one decimal place.

Study days will be calculated as follows:

- For events or findings on or after the date of the first study treatment:
 - o Study Day = Date of the event or finding – Date of the first treatment + 1
- For events or findings prior to the date of the first study treatment:
 - o Study Day = Date of the event or finding – Date of the first treatment

All dates will be displayed in DDMMYYYY format.

Two-sided hypothesis testing will be conducted for all the tests. The p-values less than 0.05 will be considered statistically significant. No adjustments of p-values for multiple comparisons will be made. No interim analyses are planned.

All statistical analysis will be conducted using SAS® version 9.4 or higher (SAS® Institute, Cary, North Carolina).

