8.2. Analysis Populations

The following populations are defined for analyses:

The Safety Population

The safety population includes all randomized subjects who receive study product.

• Per Protocol (PP) Population:

The accepted PP population used for BE evaluation includes all randomized subjects who:

- meet all inclusion/exclusion criteria,
- received and used study medication
- complete IOP evaluations for both eyes at Visit 3/Day 14 (week 2) and Visit 4/Day 42 (week 6) within the designated visit window (i.e. +/- 4 days for each visit),
- have no significant protocol violations that could have interfered with the administration of the treatment or the precise evaluation of treatment efficacy.

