5.7 Efficacy Analyses

5.7.1 Primary Endpoint

The primary efficacy endpoint is mean change from baseline in IOP of both eyes at four time points, i.e., at approximately 8:00 a.m. (hour 0; before the morning drop) and approximately 10:00 a.m. (hour 2) at Day 14 (Week 2) and Day 42 (Week 6) visits. The IOP at hour 8:00 a.m. (hour 0) on day 0 will serve as baseline for IOP at hour 8:00 a.m. for Day 14 and Day 42, while IOP at hour 10:00 a.m. (hour 2) on day 0 will serve as baseline for IOP at hour 10:00 a.m. for Day 14 and Day 42. Mean change from baseline to Day X Hour Y in IOP for each subject will be derived as the average difference IOP of (Day X Hour Y – Day 0 Hour Y) from the left and right eyes, where X = 14, 42 and Y = 0, 2.

For test formulation to be considered bioequivalent to the reference formulation, the limits of each two-sided 95% confidence interval of the treatment difference (test – reference) for mean change from baseline IOP of both eyes at all four follow-up points (i.e., at approximately 8:00 a.m. (hour 0; before the morning drop) and 10:00 a.m. (hour 2) at the Day 14 (week 2) and Day 42 (week 6) visits must be within ± 1.5 mm Hg using the PP population and within ± 1.0 mm Hg using the PP population for the majority of time points measured.

[REDACTED]

[REDACTED]

[REDACTED]

[REDACTED]

[REDACTED]

[REDACTED]

[REDACTED]

[REDACTED]

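### Does the SAP's Study Day formula, which has no Day 0, shift the Day 14 and Day 42 visit windows by one day?

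*SAP*

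**What the plan says.** SAP 5.1 introduces its rule with "Study days will be calculated as follows". From first treatment onward the rule is "Date of the event or finding – Date of the first treatment + 1". A second branch, "For events or findings prior to the date of the first study treatment", takes the plain difference in dates without the added day. The rule is given for events and findings in general, and visit windows are not mentioned.

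SAP 3.1 sets the schedule as "Visit 2/Day 0 (Baseline), Visit 3/Week 2/Day 14 (± 4 days), and Visit 4/Week 6/Day 42 (± 4 days) (End of Study".

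SAP Section 4, PP criterion (e), and the matching bullet in Protocol 8.2 require complete IOP evaluations for both eyes at Visit 3/Day 14 and Visit 4/Day 42, "within the designated visit window (i.e. +/- 4 days for each visit". Neither refers to Study Day.

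SAP 5.7.1 derives each subject's endpoint as the "average difference IOP of (Day X Hour Y – Day 0 Hour Y) from the left and right eyes", with X = 14 or 42 and Y = 0 or 2.

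**The concern.** Two day-numbering systems stand in one SAP, and nothing in the readable text maps one to the other. Study Day runs from -1 straight to 1, whereas the visits run from Day 0. An IOP reading can fairly be called a finding, so a programmer could apply the Section 5.1 formula to a visit date and test the result against 14 ± 4 and 42 ± 4. The readable text also gives no explicit anchor date for those windows.

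The stake would be PP membership. In-window IOP evaluations at both visits are a condition of entry, and both the efficacy analysis and the bioequivalence decision use the PP population. A window displaced by a day would drop some subjects who attended on time and admit some who did not. If the displacement depended on the date of the first drop, two subjects with identical visit spacing could be classified differently.

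**Working it through.** The documents state no window in Study Day units, so there is no figure to reproduce. The check is date arithmetic, followed by a comparison of the sections.

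**Inputs**
- Study Day rule: SAP 5.1.
- Nominal visits Day 0, 14 and 42, with ± 4 days: SAP 3.1 and Section 4; Protocol 8.2.
- Date of first drop: not stated in the readable text. Protocol 5.4 has the kit dispensed at Visit 2. Protocol 5.2 puts doses at about 8 am, 4 pm and 10 pm. Protocol 8.5 uses a Day 0 reading at about 10 am as a baseline. The first drop could therefore fall later on Day 0 or on the next day, and both cases are worked as assumptions.

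**Formula.** Let e be the days elapsed since Visit 2 and f the offset of the first drop from Visit 2. Then Study Day = e - f + 1 when e ≥ f, and e - f when e < f.

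**Windows counted from Visit 2/Day 0.** 14 - 4 to 14 + 4 gives e = 10 to 18. 42 - 4 to 42 + 4 gives e = 38 to 46.

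**Windows if 14 ± 4 and 42 ± 4 were applied to Study Day instead**
- f = 0: 10 ≤ e + 1 ≤ 18 gives e = 9 to 17, and 38 ≤ e + 1 ≤ 46 gives e = 37 to 45.
- f = 1: Study Day = e - 1 + 1 = e, so the windows are unchanged.

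| First drop | Study Day of Visit 2 | Study Day at e = 14 | Study Day at e = 42 | Elapsed days accepted | Wrongly out | Wrongly in |
|---|---|---|---|---|---|---|
| Visit 2 date (f = 0) | 1 | 15 | 43 | 9-17, 37-45 | 18, 46 | 9, 37 |
| Next day (f = 1) | -1 | 14 | 42 | 10-18, 38-46 | none | none |

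A shift therefore needs two premises together: windows programmed on Study Day, and a first drop on the Visit 2 date. The readable documents state neither.

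**Which scale the text uses**
1. Criterion (e) names Visit 3 and Visit 4 and relies on their designated window. That window belongs to the visit schedule, whose origin is Visit 2/Day 0.
2. The endpoint formula subtracts a Day 0 value. Visit 2 is Study Day 1 or -1 in the two cases above and never 0, so Day 0 there can only be a visit label. Day 14 and Day 42 in the same formula belong to the same scale.
3. Baseline and follow-up IOP are picked by nominal day and hour. No Study Day value enters, so the IOP changes are the same under either numbering.

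**Scale of the hypothetical.** Suppose both premises hold and attendance is a discretised normal truncated to ± 4 days. The chance of a visit on the lost day is 0.0085, 0.0285, 0.0483 or 0.0633 for an SD of 1.5, 2, 2.5 or 3 days. With independent visits, 1 - (1 - p)² gives 1.7%, 5.6%, 9.4% or 12.3% of subjects losing PP status. Uniform attendance gives 1 - (8/9)² = 21%. The attendance spread and the independence are assumptions. Truncation also leaves out anyone gained at days 9 and 37. The documents give no visit-date distribution, so these figures are not an estimate for this trial.

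**The case for a change.** The strongest case for acting is that a SAP exists to remove such choices before unmasking. Section 5.1 is worded generally and is not limited to adverse events. The first-drop date is not fixed in the readable text, and one sentence naming Visit 2 as the anchor would cost almost nothing. SAP 5.6 also adds a day when it computes treatment duration: a first drop on Day 0 and a last drop on day 46 count as 47 days although the Day 46 visit is in window.

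Part of this stands. The numbering does differ, and the readable text does not spell out the anchor. What does not stand is the step from there to a displaced window, because that requires replacing the window the PP criterion names with a variable it does not mention. The duration formula is an inclusive count of treatment days, reported as exposure, and nothing in the readable text makes it a test of the visit window. Parts of the protocol's visit procedures and schedule, and of the SAP's PP definition, are not visible in the public version, so silence in the readable text does not show that the anchor is missing.

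Removing the added day from Section 5.1 would not be a safe tidy-up either. With a first drop on the day after Visit 2, the present rule gives Study Day 14 at 14 elapsed days, whereas the altered rule would give 13 and create the mismatch it was meant to remove.

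**Conclusion.** No change to the plan follows. Read as written, the PP windows are 10-18 and 38-46 days after Visit 2, and neither the baseline nor the IOP changes depend on Study Day. The effect on the planned analysis is nil on that reading.

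A one-day displacement at each edge would arise only if Study Day were used for the windows and the first drop fell on the Visit 2 date. It would then affect only visits on elapsed days 9, 18, 37 or 46. What remains is an unstated anchor date, which the visit labels already settle for a sensible analyst and which the parts of the documents not shown may state outright. The conclusion rests on reading the designated window as that of the Day 0-based schedule, the only scale on which the endpoint formula has a Day 0.

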5.3 Demographics and Baseline Characteristics

Baseline variables (e.g., sex, age, ethnic origin) will be summarized descriptively by treatment group. Any significant baseline differences will be reviewed for their potential impact on the efficacy findings.

Continuous variable at baseline will be summarized by descriptive statistics. The summary tables will include the mean, standard deviation, minimum and maximum. For each categorical variable, the summary will include frequencies and percentages.

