5.11. Iris Color

[figure not shown]
At Screening/Visit 1, the Investigator will classify the color of the iris s Light Iris,

Dark Iris.

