6.2. Randomization Code

Randomization will be performed by a third party vendor according to a computer-generated randomization schematic where each Kit Number will be assigned one of two treatment assignments. An independent clinical packaging vendor will generate and hold the randomization codes throughout the study until formally released after database lock.

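### Does the open-ended review of significant baseline differences in SAP 5.3 need pre-named covariates and a fixed supportive analysis?

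*SAP*

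**What the plan says.** SAP 5.3 opens with "Baseline variables (e.g., sex, age, ethnic origin) will be summarized descriptively by treatment group" and adds "Continuous variable at baseline will be summarized by descriptive statistics". Between these it places the sentence at issue: "Any significant baseline differences will be reviewed for their potential impact on the efficacy findings". The section names no between-group test, no list of covariates and no analysis to follow the review. Baseline IOP is not mentioned. Nor is iris colour, although Protocol 5.11 says that at screening "the Investigator will classify the color of the iris".

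SAP 5.1 gives a general convention: "The p-values less than 0.05 will be considered statistically significant", and "No adjustments of p-values for multiple comparisons will be made". It does not apply this to any named baseline comparison. SAP 4 uses the word significant in a non-statistical sense, for protocol violations.

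Under Protocol 6.2 the packaging vendor will "hold the randomization codes throughout the study until formally released after database lock". A comparison of baseline by arm therefore comes after unmasking. This is an inference, since SAP 5.3 gives no timing.

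The decision rule is in SAP 5.7.1 and Protocol 8.5. All four 95% confidence intervals must lie within ±1.5 mm Hg, and they must lie within ±1.0 mm Hg "using the PP population for the majority of time points measured". The model text that follows in SAP 5.7.1 is blacked out.

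**The concern.** Read with SAP 5.1, the sentence seems to make a baseline p-value the trigger for re-examining efficacy. That is a poor trigger. In a randomised trial baseline differences arise by chance. What moves the treatment difference is the size of an imbalance multiplied by the covariate's relation to the outcome, and a p-value measures only the first. It can stay silent on a prognostic covariate and fire on an irrelevant one.

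The timing adds to the worry. If the review prompts an adjusted analysis, its covariates would be picked with the treatment codes known. With a pass/fail limit at 1.0 mm Hg, a reader could not tell such an analysis from one chosen for its result. At stake is how the bioequivalence result is supported or questioned in the study report. The rule itself is not affected.

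**Working it through.** The documents show no sample size, SD or primary model, so there is no figure of the plan's to reproduce. Inputs marked as assumed are illustrations.

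**1. What the review can change.** The bioequivalence rule uses only confidence limits, two margins and the per-protocol population. SAP 5.3 promises a review. It promises no adjusted model and no revised verdict, so whatever the review finds, the visible rule returns the same answer.

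**2. Whether chance imbalance makes the interval invalid.** It does not. Under randomisation the unadjusted difference is unbiased, and the variance of the change score already contains the part due to any omitted covariate. The interval therefore allows for chance imbalance. Adjustment mainly buys precision: the standard error is multiplied by √(1 − ρ²), which is 0.954 at ρ = 0.3 and 0.917 at ρ = 0.4.

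**3. The trigger, if significant means p < 0.05.** The imbalance needed is d = t(0.975, 2n − 2) × √(2/n), in SD units, for n per arm:

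| n per arm (assumed) | d |
|---|---|
| 150 | 0.227 |
| 200 | 0.197 |
| 300 | 0.160 |

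An imbalance just below d shifts the unadjusted difference by ρ × d × SD. With n = 200 and an assumed SD of change of 3.5 mm Hg, that is 0.1 × 0.197 × 3.5 = 0.07 mm Hg at ρ = 0.1, and 0.4 × 0.197 × 3.5 = 0.28 mm Hg at ρ = 0.4.

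The chance of at least one false trigger among m independent variables is 1 − 0.95^m: 14.3% for 3, 22.6% for 5 and 40.1% for 10.

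**4. How often adjustment would alter a verdict.** Simulated with normal data, a true difference of 0.2 mm Hg, SD 3.5 mm Hg and one 95% interval judged against ±1.0 mm Hg:

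| n per arm | ρ = 0.1 | 0.2 | 0.3 | 0.4 |
|---|---|---|---|---|
| 150 | 5.3% | 10.5% | 16.0% | 22.0% |
| 200 | 4.2% | 8.6% | 13.1% | 17.6% |
| 300 | 2.6% | 5.1% | 7.9% | 10.8% |

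In 84% to 88% of the altered trials the baseline p-value is 0.05 or more.

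**5. What these figures do not show.**

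- *The silent share.* About 95% of all randomised trials have p ≥ 0.05 for a given covariate, so a high share is expected in any subset. At n = 200 and ρ = 0.2, the verdict changes in 8.6% × 0.153 / 0.05 = 26% of triggered trials and in 8.6% × 0.847 / 0.95 = 7.7% of the others. The trigger is roughly threefold informative.
- *Power.* Under these inputs the unadjusted chance of meeting ±1.0 mm Hg at one time point is about 35%, 55% and 78% for n = 150, 200 and 300. Changes are common because passing is uncertain. Where the pass chance is near 90% (n = 300 with SD 3.0, or n = 200 with SD 2.5), changes fall to about 1.4% to 6.4%, and pass-to-fail changes to 1% or less.
- *Direction.* Most changes are fail to pass. At n = 200 and ρ = 0.4 a separate run gave 14.5% fail to pass against 3.7% pass to fail. That is largely precision gained, not imbalance corrected.
- *The rule tested.* The simulation uses one interval at ±1.0 mm Hg, whereas the plan needs four at ±1.5 and a majority at ±1.0. One change need not alter the overall verdict. At ±1.5 mm Hg with n = 200, changes are 1.5% to 2.9% for ρ = 0.2 to 0.4.

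**The case for a change.** The best case for amending runs as follows. The sentence is legible and refers to no other section. On either reading of significant it leaves the step open: as a p-value no planned test produces it, and as a judgement it has no criterion. The SAP exists to settle methods before unmasking. Naming prognostic covariates and one supportive model, reported whatever the baseline table shows, would cost a few lines and use data already collected.

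The description of the text stands, and so does the inference about timing. Naming covariates in advance is good practice. What does not stand is the consequence. The harm described needs an adjusted analysis that SAP 5.3 never proposes, and it would have to count against a rule that does not use it. The strongest numbers also need the p < 0.05 reading. A descriptive-only section, and the non-statistical use of the same word in SAP 4, make a reading of notable at least as natural, and then the false-trigger rates and the silent share do not apply. Finally, ANOVA and CMH are in the SAP's abbreviation list but in none of its legible analysis text. A model or baseline test may therefore sit in blacked-out text, and baseline IOP may already be in it.

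**Conclusion.** No change to the plan is called for. SAP 5.3 is loosely worded, but following it as written leaves the bioequivalence conclusion sound. An analyst would show the baseline table, comment on any imbalance in a variable believed to affect IOP, and label any adjusted model prompted by it as post hoc. Such a model could not displace the confidence-interval verdict. A pre-named supportive analysis would add context and alter no decision.

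The 3% to 22% range is an illustration only. It depends on assumed sample sizes and SD, one interval at 1.0 mm Hg, and a covariate outside the primary model. The conclusion rests on the legible decision rule in SAP 5.7.1 and Protocol 8.5, and on the blacked-out text not making the baseline review part of that rule.
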